Pembrolizumab is a potent and highly selective humanized monoclonal antibody (mAb) of the IgG4/kappa isotype designed to directly block the interaction between PD-1 and its ligands, PD-L1 and PD-L2. KeytrudaTM (pembrolizumab) has recently been approved in the United States for the treatment of patients with unresectable or metastatic melanoma and disease progression following ipilimumab and, if BRAF V600 mutation positive, a BRAF inhibitor.

CONFIDENTIAL

This document is confidential. Do not disclose or use except as authorized.

2.2.1.2 Summary of nonclinical and clinical studies.

A phase 1/2, multipart study is being conducted to evaluate the combination of the approved doses of pembrolizumab and dabrafenib and trametinib for *BRAF*V600E/K-mutant advanced melanoma. Results presented at the American Society of Clinical Oncology (ASCO) Annual Meeting June 3-7, 2016 on the nonrandomized phase 1, dose-finding part of KEYNOTE-022 showed Median days on therapy: 115 (range, 4-524). DLTs were reported in 3 out of 14 DLT-evaluable patients. Overall, 4 (26.7%) patients discontinued because of treatment-related AEs; there were no treatment-related deaths. Potentially immune-mediated AEs were reported in 6 (40.0%) patients, and included 2 cases of hyperthyroidism (1 grade 1, 1 grade 2), 2 cases of hypothyroidism (grade 1), 2 cases of uveitis (1 grade 1, 1 grade 2), and 1 case each of autoimmune hepatitis (grade 3), severe skin reactions (grade 3), and pneumonitis (grade 2). Based on observed DLTs and the AE profile, no additional dose levels were opened; pembrolizumab 2 mg/kg Q3W + dabrafenib 150 mg BID + trametinib 2 mg QD was the MTD.

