This trial has two planned cohorts, BRAFV600 mutant (cohort 1) and BRAF-wild-type melanoma (cohort 2). Treatment commences with 2 weeks of MTT (dabrafenib plus trametinib in cohort 1, trametinib in cohort 2), then two 3 weeks cycles of concomitant MTT and pembrolizumab, followed by single-agent pembrolizumab thereafter. Serial biopsies will be performed prior to MTT, and (if feasible) following the 2-week lead-in of MTT, and (if feasible) following six weeks of combination immune therapy and MTT. An optional biopsy at time of disease progression will also be performed. This trial represents a unique opportunity to not only test the effectiveness of combined immune and MTT, but also to determine which patients are most likely to benefit from this approach and, more importantly, to begin to understand why patients do or do not benefit. This valuable information that may lead to the next wave of combinatorial therapy in melanoma that involves MTT, anti-PD1 therapy, and other agents that target critical mediators of adaptive or innate resistance to combined MTT and pembrolizumab. Due to a recent shortage of research grade dabrafenib and trametinib, we plan to use commercially availability dabrafenib and trametinib. Since we cannot guarantee supply of "off-label" trametinib for cohort 2, we will open cohort 1 initially and consider

CONFIDENTIAL

This document is confidential. Do not disclose or use except as authorized.

opening cohort 2 in mid-2017, after more data is available for MEK inhibitors in patients with BRAF wild-type melanoma.

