6.2.2 Dabrafenib + Trametinib Dose Modification Requirements for **Pyrexia**

- Pyrexia is defined as a body temperature equal to or above 38.5° Celsius or 101.3° Fahrenheit
- Pyrexia is an adverse event associated with dabrafenib. In a minority of cases, pyrexia was accompanied by symptoms such as severe chills/rigors, dehydration, hypotension, dizziness or weakness and required hospitalization.
- Subjects should be instructed on the importance of immediately reporting febrile episodes.
- Pyrexia accompanied by hypotension, dehydration, renal insufficiency and/or severe (grade ≥3) rigors/chills in the absence of an obvious infectious cause should be reported as an SAE.

CONFIDENTIAL

This document is confidential. Do not disclose or use except as authorized.

Table 6-2: Dabrafenib + Trametinib dose Modification and Management Requirements for Pyrexia

Event	Management Guideline	Dose Modification

Work up:
 
 • Clinical evaluation for infection and hypersensitivity, especially if pyrexia is complicated by rigors, severe chills, dehydration, etc. • Laboratory work-up (recommend include full-blood-count, electrolytes, creatinine, BUN, CRP, liver-function tests, blood and urine culture). 
Management:
 
 • Anti-pyretic treatment should be started immediately at the first occurrence. Anti-pyretic treatment may include acetaminophen (paracetamol), ibuprofen, or suitable anti-pyretic medication per institutional standards. • Oral hydration is encouraged in subjects without evidence of dehydration. Intravenous hydration is recommended if pyrexia is complicated by dehydration/hypotension. • In subject experiencing pyrexia complicated by rigors, severe chills, etc., which cannot be controlled with anti-pyretic medication, recommend oral corticosteroids be started. • Prophylactic anti-pyretic treatment is recommended after the 2nd event. 		

1st Event:
	
 • Clinical evaluation for infection and hypersensitivity • Laboratory work-up • Hydration as required • Administer anti-pyretic treatment if clinically indicated and continue prophylactic treatment 	
 • Interrupt dabrafenib. • Continue trametinib. • Upon recovery to baseline, restart dabrafenib at the same dose level. If fever was associated with dehydration or hypotension, reduce dabrafenib by one dose level.

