13.1 Study Design/Endpoints

Primary Endpoint: The rate of clinical benefit (CBR), defined as the proportion of patients who have CR/PR/SD at the week-24 scan while remaining off MAPK-targeted therapy (MTT) after induction. To be evaluable for the primary endpoint, patients must receive at least one dose of pembrolizumab, any patient who is unevaluable for response will be classified as a non-responder.

Secondary Endpoints:

13.1.1 Overall Survival (OS): The time between the first dose of targeted therapy and death from any cause. For patients who are lost to follow-up or who have no documentation of death at the time of final analysis, follow-up will be censored at the date of last assessment of vital status.

13.1.2 Safety and tolerability: Safety and toxicity will be monitored throughout the study. An early, comprehensive safety review will be conducted at the end of the first-stage of the Simon two-stage design to review the data for unexpected severe toxicities due to the drug combination.

13.1.3 Describe temporal changes in the tumor microenvironment as a function of therapy.

Design: For each disease cohort, the Simon two-stage design is based on a type-I error rate of 0.1, at least 85% power, and a total sample size of 25 subjects. A complete safety assessment is planned to coincide with the review of clinical benefit at the end of the first stage.

Within cohort, the null hypothesis of a true CBR of 0.50 will be tested against a one-

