13.4 Analysis of Secondary Endpoints

PFS and OS: The distributions of secondary endpoints of PFS and OS will be based on the method of Kaplan-Meier. Medians of the distributions of PFS and OS will be estimated and presented with 90% confidence intervals based on log(-log(endpoint)) methodology. One-year estimates of OS will also be presented using the same methods.

Early Safety Review: An early, comprehensive safety review will occur at the end of the first stage of the Simon two-stage design and will take place when one cohort has reached the end of its respective first stage according to the Simon design. Since we do not anticipate that adverse events will differ according to BRAF mutation status, all available safety data will be combined from the two cohorts, resulting in an early safety review for up to 28 patients. All reported AEs will be summarized.

For a sample of 28 patients, there is high probability of observing at least one event if a toxicity has an incidence of at least 5%. If the true incidence of an unexpected or severe

toxicity is 5% or greater, the probability is at least 0.75 that one or more patients out of 28 will experience the toxicity during the early safety monitoring period. If the true incidence of unexpected or severe toxicity is 1% or less, the probability is 0.25 or less that at least one patient of 28 will experience the toxicity during the early safety monitoring period. 0 summarizes the probabilities of observing at least one patient with a severe or unexpected toxicity during the initial safety review for a range of true incidence rates.

Table 13.1. Operating Characteristics of Early Safety Monitoring

True Incidence of Unexpected or Severe Toxicity	Probability of Observing One or More Patients with Toxicity among First 28
1%	0.25
3%	0.57
5%	0.76
8%	0.90
9%	0.93
10%	0.95
15%	0.99

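### The early safety review pools two drug regimens on a mutation-status argument; for a toxicity specific to one regimen at most 14 patients are informative, so Table 13.1 overstates detection

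*Combined protocol and SAP*

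**What the plan says.** Section 13.4 (Early Safety Review) combines the cohorts and gives one reason: "Since we do not anticipate that adverse events will differ according to BRAF mutation status, all available safety data will be combined". The size of the pool follows in the same sentence: "resulting in an early safety review for up to 28 patients". On timing, the review "will take place when one cohort has reached the end of its respective first stage according to the Simon design". The operating characteristic, given for severe events or events not foreseen, reads: "toxicity is 5% or greater, the probability is at least 0.75 that one or more patients out of 28 will experience the toxicity". Table 13.1 gives this probability for 28 patients at incidences from 1% to 15%. Section 13.1.2 states the purpose of the review: "to review the data for unexpected severe toxicities due to the drug combination".

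The regimens are set out in section 2.3: "Treatment commences with 2 weeks of MTT (dabrafenib plus trametinib in cohort 1, trametinib in cohort 2"), with pembrolizumab added in both cohorts. Footnote a of the study calendar (section 10) repeats this.

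Three other places use a different unit:
- The synopsis (Sample Size Justification) describes the early review for 14 to 15 subjects per cohort, with a probability of at least 0.75 at 10% incidence.
- The introduction to section 13 says that the two cohorts are analysed separately.
- Section 13.6 says that safety listings and tables are presented by treatment.

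**The concern.** The premise concerns tumour genotype, but the two cohorts also differ in what they are given. Even if BRAF status had no influence on toxicity, it would not follow that a three-drug and a two-drug regimen have the same toxicity. The protocol itself ties some toxicity to the drug that only cohort 1 receives: section 6.2.2 says "Pyrexia is an adverse event associated with dabrafenib", and section 6.2.5 describes cutaneous squamous cell carcinoma with dabrafenib alone and with dabrafenib plus trametinib. No other reason for pooling is given.

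Two things are at stake. First, Table 13.1 tells the reader how likely the review is to show an unexpected severe toxicity, and it assumes that all 28 patients could show it. That fails for a toxicity confined to one regimen. Second, the review coincides with the stage 1 decision on enrolling 11 more patients, which is taken cohort by cohort. A pooled incidence describes neither regimen.

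**Working it through.** **Inputs.** Stage 1 size is 14 per cohort (section 13.1). The pooled maximum is 28 (section 13.4). Incidences are those of Table 13.1.

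**Formula.** P(at least one event among n exposed) = 1 − (1 − p)^n.

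**Step 1: reproduce the plan's figures.** With n = 28, the results at 1, 3, 5, 8, 9, 10 and 15% are 0.245, 0.574, 0.762, 0.903, 0.929, 0.948 and 0.989. Every row of Table 13.1 reproduces. The synopsis figure also reproduces: at 10%, n = 14 gives 0.771 and n = 15 gives 0.794, both at least 0.75. Each place is arithmetically right for its own n.

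**Step 2: a toxicity only one regimen can cause.** Patients on the other regimen contribute no events, so n = 14.

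| True incidence in the exposed cohort | Table 13.1 (n = 28) | n = 14 |
|---|---|---|
| 1% | 0.25 | 0.13 |
| 3% | 0.57 | 0.35 |
| 5% | 0.76 | 1 − 0.95^14 = 0.51 |
| 8% | 0.90 | 0.69 |
| 9% | 0.93 | 0.73 |
| 10% | 0.95 | 1 − 0.90^14 = 0.77 |
| 15% | 0.99 | 1 − 0.85^14 = 0.90 |

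The incidence needed for a probability of 0.75 is 1 − 0.25^(1/14) = 9.4% with 14 patients, against 1 − 0.25^(1/28) = 4.8% with 28.

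**Step 3: effect on a pooled incidence.** Suppose 14 cohort 1 patients and m cohort 2 patients are in the review, and a toxicity has incidence p in cohort 1 and zero in cohort 2. The expected pooled incidence is p × 14/(14 + m). For p = 20%:
- m = 14: 20% × 14/28 = 10% (worst case, half)
- m = 7: 20% × 14/21 = 13.3%
- m = 0: 20% (no dilution)

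As an illustration in observed counts, three events in cohort 1 are 3/14 = 21% (exact 90% CI 6% to 47%), but 3/28 = 11% (3% to 25%) in a full pool.

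**Step 4: the number actually available.** Cohort 1 opens first and cohort 2 is only to be considered later (section 2.3). The review starts when one cohort completes stage 1, so the pool lies between 14 and 28. If the lagging cohort has 7 patients, a toxicity specific to its regimen has a probability of 0.30, 0.52 or 0.68 at 5%, 10% or 15%. A toxicity common to both regimens then has n = 21, and at 5% the probability is 1 − 0.95^21 = 0.66, again below 0.76.

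**The case against.** A reader might infer that pooling hides a signal from the three-drug regimen. On the plan's own measure it does not. Table 13.1 concerns seeing at least one event, and adding cohort 2 patients cannot lower that probability. Dilution affects only a pooled incidence, and section 13.4 attaches no threshold or stopping rule to any incidence. This stands, and it limits the point to an overstated operating characteristic and a possible understatement of incidence.

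The 14 plus 14 pool is also the worst case. With cohort 1 opening first, the review may contain few two-drug patients and dilution may be small. That too stands, but in that case the 28 patients behind Table 13.1 are not there either.

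Section 13.6 calls for tables by treatment, and combined in section 13.4 could mean only that both cohorts' data enter one review. This is partial mitigation. Section 13.4 does not refer to 13.6, and its table rests on the pooled number. The synopsis already holds a per-cohort figure, which agrees with the n = 14 calculation and disagrees with 13.4 on the unit.

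It would also be wrong to infer that pyrexia or squamous cell carcinoma would be missed. Both are expected, with their own management sections, whereas the review looks for unexpected severe events. They show only that the protocol recognises toxicity tied to dabrafenib. The dose-limiting toxicities cited in section 2.2.1.2 for the three-drug combination have no two-drug comparator, so they do not show a difference between regimens.

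Finally, pooling is reasonable for toxicities of the drugs that both cohorts receive: the trametinib events of special interest in section 2.2.3.3 and the immune-related events of pembrolizumab in section 2.2.1.5. Safety does not rest on this review alone, given the monitoring committee (section 12.2) and 24-hour reporting of serious events (section 7.1).

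**Conclusion.** The point holds in a limited form. The mutation-status argument does not support pooling, because mutation status assigns the regimen. For a toxicity specific to one regimen, Table 13.1 overstates the probability of at least one event: 0.76 against 0.51 at 5%, 0.95 against 0.77 at 10%, and 0.99 against 0.90 at 15%. These figures assume 14 exposed patients, independent events and zero incidence on the other regimen; a smaller cohort at the time of review lowers them further. With both first stages full, a pooled incidence would be understated by up to half, and by less if cohort 2 is small.

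The documents do not support the conclusion that Table 13.1 is miscalculated, that pooling makes an event less likely to be seen, or that the stage 2 decision would go wrong. Opening stage 2 depends on clinical benefit in 9 or more of 14 patients within the cohort, and no safety cut-off is stated. The synopsis, section 13.4 and section 13.6 do disagree on the unit of the early review, and that needs resolving in any case.

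**What to change.** In section 13.4:
1. Replace the mutation-status premise with a statement that the cohorts receive different regimens and share trametinib and pembrolizumab.
2. Present the early safety review by cohort (regimen) first, consistent with section 13.6, and keep the pooled table as secondary, for toxicities of the shared drugs.
3. Add an n = 14 column to Table 13.1 (0.13, 0.35, 0.51, 0.69, 0.73, 0.77, 0.90) as the operating characteristic for a regimen-specific toxicity. State that 28 is the maximum for shared toxicities and that the number at the review may be lower.
4. Reconcile the text with the synopsis, so that both give the per-cohort figure (at least 0.75 at 10%) and the pooled figure (at least 0.75 at 5%) with the setting in which each applies.

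The cost is table layout, one column and a few sentences, with no added patients or data. The downside is that the stated detection probabilities become less favourable.

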13.5 Analysis of Correlative Measures

Analysis of MTT induced changes on T-cell clonality / PDL1 expression and correlation with clinical benefit. To investigate whether MTT-associated changes following a brief course of MTT can predict who will benefit from the addition of anti-PD1 therapy, assessments will be based on: (a) clonality of tumor-infiltration lymphocytes (TILs), and (b) PD-L1 IHC. TIL clonality is a term used to quantify the diversity of clones and frequency of any given clone. It is calculated by ImmunoSeq Adaptive Biotechnologies software using a clonality score, defined as $[1 - (\text{entropy}) / \log_2(\# \text{ of productive unique sequences})]$, where the entropy term takes into account the varying clone frequencies of TILs. A maximally diverse population, where every sequence is represented one time, is associated with a clonality score of zero, and a perfectly monoclonal population with a clonality score of one. Assessment times will be pre-treatment and after the 2-week MTT lead-in. Each cohort will be investigated separately.

To investigate the hypothesis that there will be an increase in TIL clonality after MTT lead-in, the overall changes in clonality of TILs after MTT will be expressed as a fold-change (2-week/pre) and compared with unity using a Wilcoxon signed-rank test with 80% power, and a 0.1, two-sided significance level. For a range of standard deviations of the fold-change between 0.8 and 1.2, we will be able to detect effect sizes between 1.4 and 1.65 for this comparison. We will further refine this question to address whether increases in clonality are related to response. Clones that comprise the largest percentage of the total T-cell population after MTT lead-in will be identified and sorted by frequency. The percentage of the overall T-cell population included in the top 5% of clones will

be compared according to response (achieving/not achieving clinical benefit) using Wilcoxon rank-sum tests. If the observed CBR is 0.75, resulting in 19 patients with clinical benefit and 6 without, a Wilcoxon rank-sum test with 0.1, two-sided significance level will have 80% power to detect a difference in percentage T-cells that is approximately 1.3 times the common standard deviation. Similar analyses will be performed for the top 2.5% or 1% of clones.

To assess if changes in clonality after MTT lead-in are associated with infiltration by new TIL clones, we will compare pre-treatment and post-MTT biopsies to identify clones that were absent from the pre-treatment biopsies, and summarize the percentage of individual clones that were identified to be new. This will be assessed for all patients in a cohort using Wilcoxon signed-rank tests, and according to clinical response using Wilcoxon rank-sum tests. In additional analyses, the percentage of pre-existing clones, rather than new clones, will be compared according to response to see if patients with high proportions of pre-existing clones after MTT lead-in exhibit a better response than patients with low proportions.

For PD-L1 expression, patients will be classified, retrospectively, into two subgroups defined by clinical benefit at 24 weeks. Fold-changes in PD-L1 IHC (2-week/pre) will be compared for patients achieving/not achieving clinical benefit using Wilcoxon rank-sum tests. If the observed CBR is 0.75, resulting in group sizes of 19 and 6, a Wilcoxon rank-sum test with 0.1, two-sided significance level will have 80% power to detect a difference in fold-changes that is approximately 1.3 times the common standard deviation.

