2.3 Rationale

It has been shown that inhibition of the mitogen-activated protein kinase (MAPK) pathway in patients with melanoma, through inhibition of BRAF and/or MEK, leads to increased melanoma antigen expression, decreased immunosuppressive cytokines, increased trafficking of CD8+ T-lymphocytes, and upregulation of immune exhaustion markers such as PD1 and PDL1. Also, in collaboration with Adaptive Biotechnologies, we have shown that patients with a higher proportion of preexisting tumor infiltrating lymphocyte clones, determined by T-Cell Receptor (TCR) rearrangement sequencing (so-called ImmunoSeq), have better outcomes with BRAF/MEKi therapy, although nearly all patients have an increase in TCR clonality in the setting of BRAF/MEKi therapy. The major conclusion from this data is that MAPK pathway targeting enhances anti-tumor immunity within the tumor microenvironment, which provides a strong rationale for combination MAPK targeted therapy with immune targeted therapy.

A number of trials of combination MAPK targeted therapy (MTT) with immune targeted therapy have been opened in recent years with mixed results. One of the major issues has been tolerability, particularly with combinations of MTT and ipilimumab. We believe that the value of combining MTT with immunotherapies, such as pembrolizumab, is that MTT may enhance immune responses in the tumor microenvironment and convert an immunologically non-responsive tumor microenvironment into an environment that is responsive to anti-PD1 immunotherapy. Thus, we are interested in testing trial designs that incorporate a lead-in phase of MTT and a brief period of concomitant MTT and immune targeted therapy.

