9. BIOMARKER, CORRELATIVE, AND SPECIAL STUDIES

9.1 Collection of Specimen(s)

Tumor biopsies are required be performed in all patients for both cohorts at four time points (as all patients are enrolled onto the first Stage of the Simon 2-stage design):

1. Prior to commencing MTT
2. Following 2-week MTT lead-in
3. Following 6-weeks of combined pembrolizumab with MTT (if feasible)
4. A biopsy at the time of disease progression will also be performed (this is optional)

Multiple cores will be obtained and/or sufficient tumor excised at each biopsy time-point, assuming that it is safe to do so (e.g. patients with rapid responses may have very little tumor to biopsy safely at the latter time points). Core biopsies or portions of the excised tumor will be processed with the following hierarchy in mind:

1. DNA/RNA/protein extraction ([name])
2. Disaggregation and flow cytometry ([name])
3. FFPE ([name])
4. Single-cell RNA seq of T cells ([name])
5. Single-cell RNA seq of tumor cells ([name])

Analysis will then be carried out to compare changes seen longitudinally and to determine if those changes are associated with improved outcomes to therapy with study treatment. Most of this work will be exploratory in nature, as analysis

CONFIDENTIAL

This document is confidential. Do not disclose or use except as authorized.

such as the technology for single-cell sequencing of tumor and T-cells is emerging and no data is presently available to inform how these analyses might be used to help predict which patients are most likely to benefit from single-agent or combination therapy. However, based on previous work, there are two assays that will be incorporated into a predictive model, PD-L1 expression by immunohistochemistry (IHC) and immuno-sequencing (immunoSEQ) using the Adaptive Biotechnologies platform.

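### The clonality score in Section 13.5 depends on how many T-cell templates each biopsy yields, so a change in yield can appear as a change in clonality

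*Combined protocol and SAP*

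**What the plan says.** Section 13.5 defines TIL clonality as 1 − entropy/log2(number of productive unique sequences) and notes that "A maximally diverse population, where every sequence is represented one time, is associated with a clonality score of zero". The test is introduced with the words "To investigate the hypothesis that there will be an increase in TIL clonality after MTT lead-in, the overall changes in clonality of TILs"; the pre-treatment and post-lead-in scores form a ratio that is "compared with unity using a Wilcoxon signed-rank test with 80% power, and a 0.1, two-sided significance level". The stated sensitivity is: "For a range of standard deviations of the fold-change between 0.8 and 1.2", "we will be able to detect effect sizes between 1.4 and 1.65".

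Two related analyses follow. The share of T cells held by the top 5% of clones after lead-in (also the top 2.5% and 1%) is compared between patients with and without clinical benefit. The plan will also "identify clones that were absent from the pre-treatment biopsies, and summarize the percentage of individual clones that were identified to be new", tested overall with signed-rank tests and by benefit with rank-sum tests.

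Two other sections bear on yield. Section 2.3 expects MAPK inhibition to bring "increased trafficking of CD8+ T-lymphocytes". Section 9.1 warns that "patients with rapid responses may have very little tumor to biopsy safely at the latter time points", and Appendix C says fewer cores may be obtainable as lesions shrink. Sections 2.4 and 9.3 say only that tissue receives survey-level sequencing under the vendor's procedures. No section gives a template count, a minimum yield, a common depth or an adjustment for T-cell number.

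**The concern.** A biopsy is a sample of the T cells in a lesion. When few templates are sequenced, most clones are seen once and the score is pushed towards zero. When more are sequenced from the same population, repeats of the common clones appear and the score rises. Dividing by log2 of the unique count does not remove this. A ratio of two scores taken at different yields therefore mixes two things: how many T cells were sampled and how unevenly they are spread over clones. Only the second is the question in Section 13.5.

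The problem is separate from the choice of ratio or test; a log scale or another paired test would carry the same bias. At stake are a powered correlative test, a stated secondary objective on the tumor microenvironment (1.3.2), and one of the two assays meant to enter a predictive model (9.1).

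**Working it through.** **1. The plan's own figure.** Inputs from 13.5: signed-rank test, two-sided 0.10, 80% power, SD 0.8 to 1.2. The number of pairs is not stated there; 25 per cohort comes from 13.2. Noncentral-t power with n scaled by the normal-data efficiency 3/π gives a detectable shift of 0.525 SD.
- 1 + 0.525 × 0.8 = 1.42
- 1 + 0.525 × 1.2 = 1.63

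This matches 1.4 to 1.65 to the nearest 0.05. With 14 pairs the range would be 1.58 to 1.87, which does not fit, so 25 pairs is used below.

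**2. The mechanism.** If 500 templates are all different, entropy = log2(500) and the score is 1 − log2(500)/log2(500) = 0, whatever the true clone frequencies are.

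**3. Size of the artefact.** Assumptions, none of them in the documents: 20,000 clones with power-law frequencies, an identical clone mix in both biopsies, and random sampling of templates. At exponent 1.0 the mean score is about 0.097 at 500 templates, 0.121 at 1,000 and 0.145 at 2,000. The false fold-changes are then 0.121/0.097 = 1.25 and 0.145/0.097 = 1.49. Ranges are over repeated runs:

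| Templates, pre to post | Exponent 1.2 | Exponent 1.0 | Exponent 0.8 |
|---|---|---|---|
| 500 to 1,000 | 1.14–1.18 | 1.23–1.26 | 1.36–1.42 |
| 500 to 2,000 | 1.31–1.32 | 1.47–1.50 | 1.89–1.92 |
| 5,000 to 10,000 | 1.09 | 1.13–1.14 | 1.24–1.25 |

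At exponent 1.0 with 500 clones, doubling from 5,000 templates gives 1.02; with 50 clones, doubling from 500 gives about 1.0. In the other direction, halving the yield from 1,000 templates gave 0.75 to 0.91 over four assumed repertoires, a false fall.

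**4. Effect on the planned test.** Take an artefact of 1.24 (a doubling from 500 templates at exponent 1.0), no true change, 25 pairs, and the plan's SD. Upward rejection is approximately P(Z > 1.645 − (0.24/SD) × √25 × √(3/π)).
- SD 0.8: (0.24/0.8) × 5 × 0.977 = 1.47, and P(Z > 0.18) = 0.43
- SD 1.2: (0.24/1.2) × 5 × 0.977 = 0.98, and P(Z > 0.67) = 0.25

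Simulated signed-rank tests on normal data give slightly less: about 40% at SD 0.8 and 22% to 24% at SD 1.2. The nominal rate in that direction is 5%.

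**5. The other two measures** (20,000 clones, exponent 1.0).
- Top-5% share of one and the same repertoire: about 0.34 at 500 templates, 0.39 at 1,000, 0.44 at 2,000. This analysis compares benefit groups at one time point, so a difference in yield between the groups confounds it.
- Clones called new when none is new: 79% at 500 pre and 500 post, 88% at 500 and 2,000, 61% at 2,000 and 500. The main driver is a shallow pre-treatment sample, and equal depth does not remove it. Section 13.5 gives no null value for the signed-rank test of this percentage.

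**6. Does down-sampling work for clonality?** Cutting both biopsies of a pair to the smaller count returned the median fold-change to 0.99 to 1.00. Rejection was 0.03 to 0.20 over 60 replicates per setting, a noisy estimate scattered around the nominal 0.10.

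**The case against.** Neither template counts nor the size of the influx appear in the documents. The artefact is modest with deep sampling and vanishes when a small repertoire is fully sampled. If every T cell in a lesion were sequenced and each clone grew by exactly the same factor, the score would not move. The vendor's software computes the score and may already normalise depth. The analysis is correlative: it does not touch the clinical benefit decision rule or the safety review, and Section 9.1 calls most of this work exploratory. All of that stands, and it limits the size and the grade of the point. It does not remove the dependence on yield, because the plan states no safeguard, and equal DNA input would not equalise T-cell counts when the T-cell fraction changes.

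A reader might infer more: that the influx expected in 2.3 will produce a false rise in clonality and an almost certain rejection. The documents do not support that. Section 2.3 speaks of trafficking, not of templates sequenced. Sections 2.4 and 9.1 and Appendix C allow tissue to become scarcer, which would reverse the bias. Simulations in which sampling is the only noise do reject in every replicate at 2 to 3 times the yield, but they ignore the plan's SD of 0.8 to 1.2. With that SD the rates in step 4 apply.

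**Conclusion.** The point holds as a risk of uncertain direction and size. As defined in 13.5, the score can move with T-cell yield alone: up if the influx raises the number of templates sampled, down if less tissue is obtained. For a doubling of yield from 500 templates, the assumed repertoires give a false fold-change of about 1.1 to 1.4, just below or touching the bottom of the planned detectable range. Fourfold yield reaches or passes that range at exponents 1.0 and 0.8. An artefact of 1.24 would be declared an increase roughly four to eight times as often as the nominal 5%. These figures rest on the assumed clone numbers, frequencies and starting yields, and on treating the artefact as a shift in normally distributed fold-changes.

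The top-clone shares are open to confounding by yield between benefit groups. New-clone percentages are inflated by shallow pre-treatment sampling even at equal depth. The plan should be amended on this point, but the primary conclusion of the trial does not depend on it.

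**What to change.** In 13.5, before any sequencing results are examined:

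1. Compute the clonality fold-change after randomly down-sampling both biopsies of a pair to the smaller productive-template count, averaged over repeated draws.
2. Compute the top 5%, 2.5% and 1% shares at one template count common to all patients, or adjust the comparison for template count. Within-pair down-sampling is not enough, because this comparison is between patients.
3. Do not rely on down-sampling for new and pre-existing clone percentages. Cutting a 2,000-template pre-treatment sample to 500 to match a 500-template post sample raises the false-new figure from 61% to 79%. Instead, compare the observed percentage with the value expected from resampling alone at the observed depths, or restrict it to clones frequent enough to have been detected before treatment. The first option also supplies the missing null value.
4. Pre-specify a minimum template count and report T-cell quantity separately as a measure of infiltration. If the vendor's software already normalises depth, say so and describe how.

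The cost is SAP wording and a short script on data the platform already produces. Some precision is lost in the deeper sample of each pair, and very low-yield samples drop out.
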